## **6. Subject Recruitment and Compensation**

We propose to enroll 249 healthy subjects consisting of Duke medical students, undergrads, surgical residents, and surgical attendings. We anticipate that 40 of the recruited participants will not complete the protocol, with 209 completing the full study. A sample size of 249 was carefully selected. This study includes three separate aims requiring new subjects for each due to the improvement in technical skill from repetition alone. Therefore, the same subjects cannot be utilized in the tDCS portion of the study as well as the gaze training or cross design study.

Prior tDCS studies have enrolled less than 20 subjects per group. For example, Reis et al 2009, which we are using as a model design, used 12 participants per group. Typical gaze training studies within surgery have had very small enrollment numbers of 5-10. Putting this together, we aimed for a cohort of 20 subjects for each intervention. The tDCS portion of the study evaluating bilateral stimulation, SMA stimulation, versus sham will require a total of 60 subjects with 20 in each study arm. As for gaze training, we need 9 subjects to help determine the expert gaze pattern. Again, 60 subjects will be required for 20 in each study arm when examining explicit, implicit, and sham gaze training. Both of these studies lead to our large cross design with four separate study arms. Therefore, a total of 80 subjects will be required for completion of Aim 3. Based on our prior experience with longitudinal designs, we accounted for attrition of about 40 subjects, resulting in a total study sample of 249.

These numbers are sufficient to obtain accurate pilot data in tDCS and gaze training in order to further direct our research going forward. The sample sizes utilized will be larger than most in published surgical education literature, which will emphasize our ability to complete thorough and novel research here at a large undergraduate and medical campus.

Participants will be recruited mostly via email to the Duke Undergraduate pre-health students and the Duke University School of Medicine general surgery interest group. Attending surgeons will also be invited to participate via email as well as in person through study staff. The Interdisciplinary Behavioral Research Center (IBRC) will also circulate the study to individuals registered in its database, according to IBRC established standards, in order to access a wider array of potential novice participants. Participants will be enrolled once they sign the approved informed consent form, at which point they will complete a questionnaire evaluating inclusion and exclusion criteria and demographics. The Duke University campus includes this large pool of possible subjects which is optimal for recruiting participants with varying exposure to surgical technical skill. Recruitment materials and the information covered by the questionnaire are provided in separate document.

Potential participants will be asked to come to the SEAL simulation lab, located on the 5th floor of the Mary Duke Biddle Trent Semans Center for Health Education. Here, they will be provided a full description of the study, asked to read and sign the consent form, and undergo a qualifying interview. The reviewed information will be obtained from the subject via face-to-face interview and will be restricted to answers to questions intended to determine whether subjects meet entry criteria. All information obtained during this review will be handled confidentially. Subjects will participate voluntarily and will be compensated \$15/hour (3 sessions in Aim 1) and \$10/hour (6 sessions in Aim 2) for their time.

## **7. Consent Process**

Section 14 question have been completed on the e-IRB submission form.

Written Informed Consent will be obtained from each subject prior to enrollment into the study. Separate consent forms have been developed for tDCS, gaze training, and the identification of expert gaze pattern. A fourth consent will be developed later for the cross-design study in a way that will keep subjects blinded. However, this will require outcomes from Experiments 1 and 2 above first. All potential subjects will be informed as to the purpose of the study and the potential risks and benefits known, reasonably predicted, or expected. Once a subject has been consented, the screening process will begin. Verification consists of a detailed interview with the participant to obtain a neurologic and psychiatric history of illness as well as surgical exposure and experience. The Investigator will retain the original copy of the Informed Consent Form signed by the patient, a duplicate will be provided to the patient. Only the consent form approved by the IRB will be used.

## **8. Subject's Capacity to Give Legally Effective Consent**

Potential subjects who do not have the capacity to give legally effective consent will not be included in this study.

## **9. Study Interventions**

### **9.1. Fundamentals of Laparoscopic Surgery procedure**

To evaluate expert performance and the effectiveness of each training intervention, this study will utilize a portion of the Fundamental Laparoscopic Skills (FLS) curriculum. FLS is a curriculum that targets basic laparoscopic skills required for success in the variety of operations that are performed with the minimally invasive technique. The FLS curriculum has been validated as translatable to the operating room, and completion is required by The American Board of Surgery to be eligible for certification. FLS consists of five pre-defined skill modules with timed assessments. The current study will utilize only FLS module 1 (module 1 for Aim 1, both modules for Aim 2 and Aim 3) which are performed on the standard laparoscopic box trainer. Based on the average times for completion as well as the average number of repetitions required to achieve proficiency, both of these skills are developed over a prolonged time period making them ideal training models for this study.

FLS module 1 is the Peg Transfer task in which two Maryland dissectors are used to move 6 objects from the subject's left side of the pegboard to the right and back. The transfer between hands must be done in the air without assistance from the pegs. Time penalties are incurred if the object is dropped outside the field of view. Timing stops upon release of the last object.

In the current study pending the Aim, these two modules will be used as both the assessment benchmarks and as the training tasks. As illustrated in **Table 1**, each participant will perform four 20-minute training sessions on the tasks over one to three weeks while

receiving their group-specific augmentation. If the participant is in Experiment 3, an additional follow up session will be scheduled approximately 4-6 weeks after the end of the main training procedure to evaluate retention of learned skills.

Visit 1	Visit 2	Visit 3	Visit 4	Visit 5	Visit 6
90 minutes	60 minutes	60 minutes	60 minutes	60 minutes	60 minutes
Introduction Screening Consent Videos Acclimation Pretest Task A – 20min Break 5 min Task B – 20 min	Acclimation Task A – 20min Break 5 min Task B – 20 min	Acclimation Task A – 20min Break 5 min Task B – 20 min	Acclimation Task A – 20min Break 5 min Task B – 20 min	Acclimation Task A – 20min Break 5 min Task B – 20 min	Acclimation Task A – 20min Break 5 min Task B – 20 min Posttest

**Table 1:** Experimental protocol and activities. Tasks A and B correspond to the FLS module 1, which will be counterbalanced over participants and sessions pending Aim. All 3-6 visits will occur within 1-3 weeks, again pending Aim. An additional follow up visit (not shown here) will occur at approximately 4-6 weeks for participants in Exp 3.

Prior to the start of FLS activities, each participant will begin by watching two videos demonstrating how to correctly complete FLS modules 1 and 5 (links below). After watching these videos, participants will be instructed by the experimenter on how to use the device and will have the opportunity to practice 2-4 trials to become familiar with the equipment before starting the experiments. In order to carry out quantitative assessment of the training interventions, video will be recorded directly from the box trainer video screen (showing only the tools and the FLS objects). This video will be coded to document the number of repetitions, completion times, and FLS scores for each task.

Data collected from these FLS modules will provide the core dependent variables in our analyses. This will include the number of repetitions and completion times for each of the tasks performed during the sessions. Progress through each of the training sessions and over multiple training sessions will be recorded in the form of behavioral learning curves. Completion times will be based upon official FLS scoring utilizing video coding for most accurate data.

FLS video modules:

<https://www.youtube.com/watch?v=gAQPXHWqdXQ>

## 9.2. Transcranial Direct Current Stimulation (tDCS) Procedure (Experiment 1)

Transcranial direct current stimulation is a noninvasive neuromodulatory technique that delivers constant, low-intensity, direct current to cortical areas via electrodes placed on the scalp. Over the past 10 years, numerous studies have shown that this approach can be used

to facilitate or inhibit spontaneous neuronal activity and there are a growing number of studies that have demonstrated tDCS can enhance motor learning in healthy individuals as well as speed recovery in clinical populations. Further, the ease with which tDCS can be implemented and tolerated, paired with the lasting changes in cortical excitability it induces, gives this approach powerful potential to facilitate surgical skill learning.

Participants in this study will be randomly assigned to receive one of four tDCS conditions (2 electrode configurations, each with active or sham) administered using the Soterix 1x1 clinical trial device. All individual tDCS stimulations will take place in 20-minute blocks, with a 5-minute break between each block. Current will be delivered through saline-soaked sponges (3 cm x 5 cm) that will be re-wetted with saline when needed during the experiment and in the breaks between blocks to prevent skin irritation and increase impedance.

There will be two active tDCS conditions:

1. Bilateral configuration tDCS, with anode over the left motor cortex, and cathode over the right motor cortex, corresponding to C3 and C4 10-20 EEG sites, respectively;
2. Supplemental motor area (SMA) configuration tDCS, with anode over the SMA (3 cm anterior to the vertex), and cathode over midline prefrontal cortex (Fpz).

The two sham tDCS conditions will utilize the same two electrode configurations (50% of each across participants). In both active and sham conditions, the current will be initially increased in a ramp-like fashion over 30 seconds until reaching 2 mA. During the active conditions, the current will be maintained for 20 minutes, while in the sham condition it will be turned off after 30 s. This initial current ramp-up allows us to reproduce the perceived sensations on the skin (tingling, fade) induced by the active tDCS and thus, create an effective placebo condition.

### 9.3. Expert Gaze Tracking Procedure (Experiment 2a)

Gaze tracking is an approach by which movement of the pupils is measured to infer where people are looking. In the current study this will be achieved by wearing the Mobile Eye head-mounted tracking system from Argus Science. This wearable device tracks the pupil as well as the scene at 30 Hz. This data is then analyzed via the ETAnalysis software on a connected laptop. This software is able to produce discrete gaze points, gaze patterns, heat maps, and peek maps. These patterns and maps can then be exported to a secure server and reproduced for viewing by study staff and subjects in particular for explicit training described below.

Gaze tracking will be initiated by recruiting a sample of 9 participants, including three attending surgeons, three surgical residents, and three novices in order to deduce the expert eye movement patterns specifically for FLS task 1. Each of the three cohorts will train to proficiency on each of the tasks as defined by FLS guidelines (average of 48 seconds for task 1). Participants will be allowed to practice as much as needed in order to achieve this level of proficiency. However, they will not be asked to practice more than 10 hours. We hypothesize

that attending surgeons and senior residents will achieve proficiency quickly while novices will require the average amount of repetitions to reach proficiency (57 repetitions on task 1). Once proficiency standards are met, each subject will undergo testing with gaze tracking.

Testing will take place in a 20-minute session in which they will complete the single FLS task repeatedly for 20-minutes. Gaze position will be calibrated using the Argus ET Mobile device before the gaze will be tracked for the duration of the active 20-minute session. This procedure will yield continuous information about the position of the pupils in relation to the scene in front of them for all repetitions completed.

Video recording of the performance will be coded as described above to collect number of repetitions, completion times, and FLS scores for each task. The subject, regardless of initial cohort, with the fastest time and best FLS score will be deemed the expert gaze pattern, and that pattern will be used in the following experiments to help train novices more efficiently.

#### 9.4. Gaze Training Procedure (Experiment 2b)

Surgical novices will participate in the gaze training procedures. These individuals will be randomly assigned into implicit learning, explicit learning, or control training groups.

The *explicit training group* will review the expert gaze pattern videos for both FLS tasks with a member of the study staff. Together they will discuss where the expert gaze focuses throughout the tasks. The subject will then complete a 45-minute training session consisting of 20-minutes of FLS task 1, a 5-minute break, and 20-minutes of FLS task 5. The subject will complete as many repetitions of the task as time allows. Between training sessions, the study staff will process the subjects' gaze patterns from the prior session. The subject along with a member of the study team will review the expert gaze pattern as well as the subject's previous performance before starting each subsequent training session.

The *implicit training group* will complete the same regimen as described above. However, they will not receive explicit instructions on the expert gaze pattern. Instead, they will perform the FLS tasks with a contrast mask superimposed on the video screen. This mask will be derived from the expert gaze pattern obtained in Stage 1 and will consist of a moving opacity occlusion that allows for transparent viewing of 1-degree of visual angle around the fixation points, while masking the rest of the screen with an 80% contrast mask. The transparent area of interest will progress through the task until completed by the subject. Participants will complete as many repetitions as possible during 20-minutes of training on one of the tasks, followed by a 5-minute break, then another 20 minutes on the other task. Task order will be counterbalanced across participants and all 6 training sessions.

The *control group* will perform the same tasks, 20-minutes each, without review of gaze pattern or implicit mapping.

All subjects will complete a total of six 60-minute training sessions over a 3-week period.

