##### **Experiment 2:** Determine if gaze training can accelerate the learning of laparoscopic skills.

In this experiment we will first establish expert gaze patterns in the Fundamentals of Laparoscopic Surgery modules 1 and 5 by testing a total of 9 participants, including attending surgeons, senior residents, and novices trained to proficiency. We will then compare behavioral learning curves from non-expert participants without gaze training against those trained using both explicit (by reviewing the expert gaze pattern) and implicit gaze (by using a visual mask during the training, leading the participant to follow the expert gaze) derived from the expert gaze patterns. This will be tested in 3 groups of 20 participants, who train for 40-minutes in each of 6 sessions that occur within 3 weeks.

We hypothesize that both explicit and implicit gaze training will lead to faster skill acquisition with implicit greater than explicit. These training sessions will be measured by trials required to gain proficient module completion scores relative to the group of participants who practice without any gaze training.

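### Experiment 2 is scored on training trials that only the implicit arm performs through a mask, so both contrasts involving that arm mix learning with the mask's immediate effect

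*Combined protocol and SAP*

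**What the plan says.** Section 4 (Experiment 2) plans three groups of 20: explicit gaze training, implicit gaze training and no gaze training. The hypothesis is directional: "We hypothesize that both explicit and implicit gaze training will lead to faster skill acquisition with implicit greater than explicit". The measure attached to it is taken in training: "These training sessions will be measured by trials required to gain proficient module completion scores", relative to the group without gaze training. Section 9.1 counts among its core dependent variables the "number of repetitions and completion times for each of the tasks performed during the sessions". Section 12 names completion times and error rates in the drills, analysed by a mix of analysis of covariance and growth curves. It gives no time point, time scale or rule for masked trials.

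Section 9.4 describes what each arm does in those trials.

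- **Implicit:** "they will perform the FLS tasks with a contrast mask superimposed on the video screen". A window of 1 degree of visual angle around the expert's fixation points stays clear, "masking the rest of the screen with an 80% contrast mask". Practice is by time, not by count: "Participants will complete as many repetitions as possible during 20-minutes of training on one of the tasks".
- **Explicit:** expert gaze videos, and later the participant's own earlier gaze, are reviewed before the session. No mask is described.
- **Control:** this group "will perform the same tasks, 20-minutes each, without review of gaze pattern or implicit mapping".

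Table 1 lists a Pretest at Visit 1 and a Posttest at Visit 6. Section 4 ties the mask to practice ("by using a visual mask during the training, leading the participant to follow the expert gaze"), which suggests that both tests are unmasked, but no section says so. Section 9.5 chooses the more effective gaze variant for Experiment 3 from the earlier results, without saying which results. The only assessment stated to be free of intervention is the 4-6 week follow-up in Experiment 3.

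**The concern.** The mask does two things at once. It is meant to teach a gaze pattern, and it changes how hard the current trial is. A masked trial can be slower because most of the screen is obscured, or faster because the clear window shows where to look. Neither result alone shows that less or more has been learned, yet the plan's measures count it as learning.

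Two of the three hypothesised contrasts use the implicit arm, including the one that ranks the two gaze variants. If that ranking feeds the choice for Experiment 3, a variant dropped because of the mask cannot be recovered there. Unmasked performance that was never scored cannot be reconstructed afterwards.

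**Working it through.** **1. Which contrasts are affected**

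| Contrast | Viewing condition of scored training trials | Mask effect in the contrast? |
|---|---|---|
| Implicit vs control | masked vs full screen | yes |
| Implicit vs explicit | masked vs full screen | yes |
| Explicit vs control | full screen vs full screen, as described | no |

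**2. Inputs.** The plan gives no power calculation, variance or mask effect for Experiment 2, so there is no figure of its own to reproduce here. Section 9.3 supplies two anchors for task 1: proficiency is an average of 48 s, and novices need 57 repetitions on average. It supplies nothing for task 5. The curve shapes, starting times T1, plateaus A and mask effects below are assumptions. Errors are ignored and learning per trial is identical with and without the mask.

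**3. Trials to proficiency.** Let the mask multiply each trial's time by m. The masked participant records 48 s when the underlying time is 48/m: 43.6 s for m = 1.10 and 53.3 s for m = 0.90.

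*Power curve:* T(n) = T1 × n^(-b), with b = ln(T1/48)/ln 57. The crossing is at n = 57 × m^(1/b).

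*Plateau curve:* T(n) = A + (T1 - A) × exp(-k(n - 1)), with k = ln[(T1 - A)/(48 - A)]/56. The crossing is at n = 1 + ln[(T1 - A)/(48/m - A)]/k.

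| Curve | Rate | m = 1.10 | m = 0.90 |
|---|---|---|---|
| Power, T1 = 120 s | b = 0.227 | 86.8 | 35.8 |
| Power, T1 = 240 s | b = 0.398 | 72.4 | 43.7 |
| Plateau, A = 35, T1 = 120 s | k = 0.0335 | 69.2 | 46.8 |
| Plateau, A = 35, T1 = 200 s | k = 0.0454 | 66.0 | 49.4 |
| Plateau, A = 40, T1 = 120 s | k = 0.0411 | 76.2 | 44.6 |
| Plateau, A = 40, T1 = 200 s | k = 0.0535 | 71.7 | 47.4 |

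A 10% slowing thus moves 57 to about 66-87, and a 10% speeding to about 36-49, with no difference in learning.

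**4. Repetition counts.** A block lasts 20 × 60 = 1200 s. Ignoring reset time, a 48 s performer completes 1200/48 = 25.0 trials. At m = 1.10 the count is 1200/52.8 = 22.7, and at m = 0.90 it is 1200/43.2 = 27.8.

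**5. Growth curves.** If masked time is m × T(n), its logarithm is ln m + ln T(n). The slope per trial on the log scale is unchanged and only the level moves. On the raw scale every slope is multiplied by m. If m changes as participants adapt to the mask, the log slope changes too. Section 12 specifies neither the log scale nor the slope as the comparison.

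**The case against.** The strongest reply is that the plan already holds the ingredients of a sound comparison. Table 1 has a Pretest and a Posttest, section 4 confines the mask to training, and analysis of covariance suits a Pretest-adjusted Posttest. On that view only a sentence is missing. It stands in part: the two tests are probably unmasked, so a reader should not infer that Experiment 2 has no usable unmasked assessment. But the measure stated with the hypothesis is itself taken from masked trials, and nothing gives the two tests a role in these contrasts or in the variant choice.

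A second reply is that growth-curve slopes absorb a constant mask effect. That holds for a constant percentage effect with log time against trial number. It does not rescue trials to proficiency, which depends on a fixed threshold.

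A third is that the mask is the intervention, so its effect belongs in the result. It belongs there as far as it changes skill; the hypothesis concerns skill acquisition, not performance while masked.

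Finally, section 6 presents the sample sizes as adequate for pilot data, and a variant wrongly chosen would still face an intervention-free follow-up in Experiment 3. That is fair, but a variant wrongly discarded gets no such test.

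**Conclusion.** The concern holds. Analysed as written, implicit versus control and implicit versus explicit cannot be read as differences in learning. The Experiment 3 gaze choice would probably inherit the problem; this is an inference, because section 9.5 does not say which results decide. Explicit versus control is sound on this point.

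The size is unknown. The shifts from 57 to 66-87 or to 36-49 are illustrations for task 1 only. They rest on the assumed curves, a constant 10% mask effect and equal learning per trial.

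Three stronger readings are not supported. One might infer that the mask handicaps the implicit arm, but the documents give no direction. One might infer that the wrong variant will be chosen, but that depends on an effect nobody has measured and on an unstated selection measure. One might want a false-positive rate, but any such rate would reflect assumed variances, curves and mask effects, and a reading of proficiency that section 9.3 frames as an average rather than a single trial.

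**What to change.** 1. In section 9.4 and Table 1, state that the Pretest and Posttest are done without the mask in all three arms, with the same fixed number of scored trials per task.
2. In section 12, base implicit versus control, implicit versus explicit and the Experiment 3 gaze choice on the unmasked Posttest, adjusted for the Pretest.
3. Report the implicit arm's masked training curves and trials to proficiency descriptively. Explicit versus control can keep trials to proficiency.
4. If the implicit variant goes forward, apply the same rule in section 9.5.

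This is a change of wording, with no extra participants or visits. Its real cost is that a Visit 6 test measures level, not speed, and may miss a difference if the arms have converged. Suppose one arm truly learns 25% faster (48 s at about 46 trials). On the plateau curves above, the gap peaks at about 9-21 s around Visits 2-3 and falls to about 0.3-1.7 s by the end of Visit 6. On the power curves about 3-5 s remains.

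Optional, to reduce that loss: score a few unmasked trials per task at Visits 2-6 in all arms, for example in the existing Acclimation slot. State the time scale and report results both by visit and by cumulative repetitions, because a mask that changes trial time also changes practice volume. These trials slightly dilute the implicit training, and their fit must be checked. The blocks and break take 20 + 5 + 20 = 45 of 60 minutes. The remaining 15 must also hold Acclimation, the explicit arm's gaze review if it falls within the visit, and the Posttest at Visit 6. Task 5 times are not given.
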